6.10.3 Biomarker and Pharmacogenomic Parameters

Exploratory biomarker and pharmacogenomic analyses are to be performed using the pharmacodynamic analysis set. Summary statistics for serum total FKN concentration, measured faecal calprotectin and serum CRP levels, change and % change from baseline are to be calculated by treatment group and evaluation time.

CCI

Details and results of the analysis of blood CD16⁺ monocytes, etc. and blood CD16⁺ monocytes etc. genetic markers are to be reported in a separately created report, and not included in the Clinical Study Report

6.10.4 Immunogenicity Analysis

The incidence and ratio of serum anti-E6011 antibodies are to be calculated by treatment group and evaluation time. If anti-E6011 antibodies are confirmed, frequency and ratio of their neutralizing activity (if present) and isotypes are to be calculated.

6.10.5 PK-PD Relationships

PK-PD relationships will be explored graphically, the geometric mean serum E6011 concentration time profile and PD biomarker time profile will be displayed in the same graph on linear and semi log scales by dose. These plots will be generated by race (all patients, and by Japanese and non-Japanese patients).

Different endpoints and the corresponding PD biomarker will be displayed as a scatter plot and correlation coefficients should be calculated:

- E6011 concentrations
- CDAI
- PRO2
- SES-CD

These plots will be generated by race (all patients, and by Japanese and non-Japanese patients).

6.11 Modifications from the Statistical Section in the Protocol

There are no modifications from the statistical section in the protocol.

7 INTERIM ANALYSES

NA

8 SAMPLE SIZE AND POWER CALCULATIONS

The number of subjects in this clinical trial was determined considering stimulation-generated operating characteristics relating to efficacy assessment, based on efficacy outcomes of the 101 trial and of similar drugs. With 20 subjects allotted to each group, if the actual difference in CR100 response rate between the E6011 group and placebo group is 40% or more, the probability of confirming the efficacy of E6011 is above 80%.

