#### **Anticipated Number of Subjects**

40 completed patients (20 patients in the E6011 groups and 20 patients in the placebo group)

- 22 Japanese patients: 18 non-Japanese patients
- 8 biologic-naïve patients

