# 9.7.2 Target sample size

The number of subjects in this clinical trial was determined considering stimulation-generated operating characteristics relating to efficacy assessment, based on efficacy outcomes of the 101 trial and of similar drugs. With 20 subjects allotted to each group, if the actual difference in CR100 response rate between the E6011 group and placebo group is 40% or more, the probability of confirming the efficacy of E6011 is above 80%.

The number of enrolled subjects was 25 at the end of the recruitment. Therefore, the sample size will be reduced to 25 subjects, but the analysis plan will remain unchanged and performed in accordance with section 9.7 Statistical method.

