[REDACTED] Details and results of the analysis of blood CD16⁺ monocytes, etc., blood CD16⁺ monocyte, etc. genetic markers and blood biomarkers (comprehensive proteome analysis) using the residual serum collected for this study are to be recorded in a separately created report, and not included in the Clinical Study Report.

Immunogenicity

Immunogenicity is to be analyzed using the safety analysis set. Incidence and ratio of serum anti-E6011 antibodies are to be calculated by treatment group and evaluation time. If anti-E6011 antibodies are confirmed, frequency and ratio of their neutralizing activity (if present) and isotypes are to be calculated.

Safety

Safety is to be analyzed using the safety analysis set. Summary statistics related to safety data (sample size, mean value, standard deviation, median value, minimum and maximum as continuous variables; sample size and ratio as categorical variables) are to be calculated by each treatment group based on the treatment that was administered. Safety endpoints include adverse events, clinical examination values, vital signs, weight, physical examination, standard 12-lead ECG tests, neurological symptoms and blood CD4⁺ cell count.

- Incidence rate of adverse events that occurred after the IMP administration is to be calculated by treatment group.
- Summary statistics for measured clinical examination values, vital signs and CD4⁺ cell count, as well as their change from baseline, are to be calculated by treatment group.
- For standard 12-lead ECG test findings and neurological symptoms, the numbers and rates are shown in the shift table by each treatment group and by normal and abnormal findings.

Interim analysis

No interim analysis is planned in this clinical trial.

Sample size Justification

The number of subjects in this clinical trial was determined considering operating characteristics pertaining to a simulation efficacy evaluation, with reference to efficacy performance in the E6011-J081-101 study, as well as efficacy performance of similar drugs. With 20 subjects allotted to each group, if the actual difference in CR100 response rate between the E6011 group and placebo group is 40% or more, the probability of confirming the efficacy of E6011 is above 80%.

Study schedule and anticipated date of completion

Recruitment: September 2018 to Mar 2022

Treatment: October 2018 to April 2022

Follow-up: Jun 2021 to April 2024

Close-out: May 2024

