3.1 Study Population

Patients with Crohn's disease ranging from moderate to severe aged 18 or over and under 65 on the date of consent, diagnosed with small intestine-type, small and large intestine-type, or large intestine-type Crohn's disease at least 12 weeks before giving consent and that meet the rest of the inclusion/exclusion criteria

Approximately 40 subjects will be included in this clinical trial.

- E6011 group 20 subjects: Placebo group 20 subjects
- 22 Japanese subjects: 18 non-Japanese subjects (rough estimate)
- 8 biologic-naïve patients (rough estimate)

Subjects that meet all the following inclusion criteria and do not fall under any of the exclusion criteria shall receive the IMP.

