6 STATISTICAL METHODOLOGY

This analysis plan gives a detailed description of the statistical methodologies, data listings, summary tables, and figures planned in the analyses of the data in the E6011-ET2 study.

This section describes the statistical analyses of the study based on the statistical section of the English protocol v10 17SEP2021. Any differences with the protocol will be identified and documented.

The statistical data analyses, described in this document, are intended to provide unbiased and valid conclusions concerning the objectives of the study.

This SAP describes only the analyses for the study objectives not involving the pharmacokinetic objectives. These will be described in a separate analysis plan.

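### The sample size was cut to 25 with the decision rule kept, but the SAP and both synopses still rest on 20 per group, and no success probability is given for 25

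*SAP*

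**What the plan says.** Protocol 9.7.1.6.1 and SAP 6.8.1 define the primary decision. Efficacy counts as confirmed if the posterior probability that the Week 12 CR100 rate on E6011 exceeds placebo by at least 25 points is 50% or more. SAP 6.8.1 sets Jeffreys Beta(1/2, 1/2) priors in each arm.

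The size statements are:

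- **Protocol 9.7.2 (v11.0, 18 April 2022):** repeats the 20-per-group rationale, then reports 25 enrolled and says "the sample size will be reduced to 25 subjects, but the analysis plan will remain unchanged".
- **Protocol synopsis:** "40 completed patients (20 patients in the E6011 groups and 20 patients in the placebo group", and a justification based on 20 per group. Protocol 9.3 also still says about 40.
- **SAP 3.1:** "Approximately 40 subjects will be included in this clinical trial", 20 per arm.
- **SAP 1 and SAP 8:** "With 20 subjects allotted to each group" and a true difference of 40 points or more, "the probability of confirming the efficacy of E6011 is above 80" per cent.
- **SAP 6:** the plan is "based on the statistical section of the English protocol v10 17SEP2021", and "Any differences with the protocol will be identified and documented". SAP 6.11 then reports: "There are no modifications from the statistical section in the protocol".

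**The concern.** The figure of 80% is the only operating characteristic in either document, and it is conditional on a sample size that was not reached. The rule was kept for 25 patients without a new figure. The chance of meeting the rule when E6011 does nothing is not given at any size.

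Meeting the rule is worded as confirmation of efficacy, in a trial that Protocol 9.4.4 describes as a pivotal proof of concept. To weigh a positive or negative result, a reader needs to know how often 25 patients would produce it under the hoped-for effect and under none.

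The documents also disagree on size. A version gap may explain the SAP, which follows protocol v10 and whose own date is not visible. It does not explain why v11.0 gives 25 in section 9.7.2 and 40 in its synopsis and section 9.3.

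**Working it through.** **Inputs from the documents.** Rule: P(p1 − p2 ≥ 0.25 | data) ≥ 0.50, where p1 is E6011 and p2 is placebo. Prior: Beta(0.5, 0.5) per arm. Planned size: 20/20. Enrolled: 25, randomised 1:1. Target difference: 40 points. Missing outcomes count as non-response.

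**Assumptions.** Neither the placebo CR100 rate nor the split of the 25 is given. I took placebo rates of 5% to 55% in 1-point steps and E6011/placebo splits of 13/12, 12/13, 14/11 and 11/14. I added 12/12 for the case where one patient falls outside the full analysis set.

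**Method (exact, no simulation).**

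1. With x1 of n1 and x2 of n2 responders, the posteriors are independent: p1 ~ Beta(x1 + 0.5, n1 − x1 + 0.5) and p2 ~ Beta(x2 + 0.5, n2 − x2 + 0.5).
2. The posterior probability is the integral over p2 of f(p2) × P(p1 ≥ p2 + 0.25), done numerically. An outcome is a success if this is at least 0.50.
3. The probability of success is the sum of Bin(x1; n1, p1) × Bin(x2; n2, p2) over all successful outcomes.

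Example at 20/20 with 4 placebo responders: 10 responders on E6011 give 0.610 (success), and 9 give 0.473 (failure). The rule there needs 6 more responders on E6011, or 6/20 = 30 points. At 13/12 it needs 4 more for 0 to 6 placebo responders, then 5. At 12/13 it needs 4 more for 0 to 2, then 3. At 12/12 it needs 4 more throughout. No outcome lies closer than 0.003 to the 0.50 threshold, so numerical error does not affect the classification.

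**The plan's own figure.** At 20/20 and a 40-point difference, the probability of success is 80.7% to 84.9%, lowest at a placebo rate of 30%. The statement of more than 80% reproduces.

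**The reduced trial, true difference 40 points.**

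| Split (E6011/placebo) | Range, placebo 5–55% | Placebo 10 / 20 / 30% | Above 80% when placebo is |
|---|---|---|---|
| 20/20 | 80.7–84.9% | 83.2 / 81.3 / 80.7% | 5–55% (all) |
| 13/12 | 75.0–81.7% | 80.8 / 80.3 / 80.6% | 5–37% |
| 12/13 | 75.0–81.7% | 75.5 / 79.3 / 80.6% | 23–55% |
| 14/11 | 75.4–79.4% | 76.7 / 77.1 / 76.7% | never |
| 11/14 | 75.4–79.4% | 77.4 / 75.4 / 76.7% | never |
| 12/12 | 72.5–75.7% | 74.4 / 72.9 / 72.5% | never |

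The true difference needed for at least 80% at every placebo rate in the range is 40 points at 20/20, 43 points at each of the four splits of 25, and 45 points at 12/12.

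**No true difference.** The chance of meeting the rule, over common rates of 5% to 95%:

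| Split | Maximum (common rate near 50%) | Common rate 20% | Common rate 30% |
|---|---|---|---|
| 20/20 | 4.0% | 1.4% | 2.8% |
| 13/12 | 11.3% | 4.8% | 8.0% |
| 12/13 | 11.3% | 3.5% | 7.3% |
| 14/11 | 9.5% | 4.0% | 6.2% |
| 11/14 | 9.5% | 4.8% | 6.9% |
| 12/12 | 7.6% | 3.6% | 5.8% |

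The maximum rises by a factor of 7.6/4.0 = 1.9 to 11.3/4.0 = 2.8.

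**The case against.** The 20-per-group sentence is a conditional planning statement. It was true when written, and Protocol 9.7.2 itself keeps it beside the reduction to 25, so short recruitment does not make it false. The reduction is disclosed. SAP 6.11 may have been accurate against protocol v10, which is not available here. SAP 6.1 calls the analysis exploratory and neither document promises an error rate. The loss can be negligible: at 13/12 and placebo rates of 10% to 30%, the probability of success is still just above 80%. Part of the spread between splits is discreteness, since 13/13 gives 79.3%, 77.6% and 77.0% at placebo rates of 10%, 20% and 30%, all lower than 13/12 with one patient fewer. The 11.3% maximum needs a common response rate near 50%; at 10% it is about 1% for the near-even splits. Recruitment is over, so no calculation can change the design.

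Most of this stands and limits the point. It supports not assured, rather than below 80%, and it rules out calling the planning sentence an error. It does not answer the remaining gap: the condition behind the only stated figure no longer holds, nothing replaces it, and v11.0 gives two sample sizes. The exploratory label does not remove the need, because the rule still ends in a declaration that efficacy is confirmed.

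**Conclusion.** The point holds. The plan states a size and a success probability that the reduced trial does not reliably deliver. The loss is moderate: at most about 5 points below 80% for the splits of 25 examined, and 7.5 points at 12/12. In some cases there is no shortfall. The larger relative change is in the chance of meeting the rule with no true effect, which roughly doubles to triples at its maximum.

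The figures rest on the assumed splits and placebo rates and on the Jeffreys prior in SAP 6.8.1. They count every patient in the stated split as evaluable or as a non-responder; further exclusions from the full analysis set would reduce the numbers again. Whether SAP 6.11 was wrong when written cannot be settled. Against v11.0 it does not hold for the sample size.

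**What to change.** In SAP 8, or in the CSR if the remission-induction database is already locked:

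1. State the enrolled size of 25 and label the 20-per-group sentence as the original planning rationale, with the same label on the matching sentence in SAP 1.
2. For the realised allocation and a stated range of placebo rates, give the probability of meeting the criterion at a 40-point difference and at zero difference.
3. In the same SAP revision, correct the headcount in SAP 3.1, the v10 reference in SAP 6 and the statement in SAP 6.11.
4. Align the protocol synopsis and section 9.3 if the protocol is revised again. If it is not, the CSR should note the discrepancy.

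Optionally, and separately, report a 95% credible interval for the difference beside the posterior probability of a difference above zero that SAP 6.8.1 already plans.

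The cost is a few sentences and one short exact calculation. Enrolment and the decision rule stay as they are, and no separate protocol amendment is needed, so there is no extra ethics review. The stated probability of success becomes slightly less favourable.

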9 STATISTICAL SOFTWARE

All statistical analyses, listing, tabulations and figures will be produced using SAS® Version 9.4 or later through fully validated and 21 CFR Part 11 compliant SAS Drug Development V3.3 interface.

10 GENERAL FORMAT OF TABLES, FIGURES AND SUBJECT DATA

Tables and listings will be produced in accordance with the principles outlined by the ICH E3 guideline. All summary tables will be presented by treatment group and race (all, Japanese and non-Japanese).

The design of the tables will be clear and concise so that comparative reading is easily possible.

All descriptive variables will be tabulated. Quantitative variables will be described showing their number of available and missing observations, mean and its CI (95% level), median, standard deviation, the range (minimum and maximum) and the first and third quartiles. Frequency and percentage will describe qualitative variables.

Missing values will be tabulated with their frequency but will not be included in the calculation of percentages. Analysis will be based on observed cases, i.e., no replacement of missing data is planned in general except otherwise planned in the appropriate statistical methodology section (section 11, section 12 or 14).

Pharmacokinetic data (E6011 serum concentrations) will be summarized by treatment group and race (All, Japanese and Non-Japanese) and evaluation time, including the number of sample results, minimum, medium, maximum, mean, standard deviation and coefficient of variation (CV). In addition, geometric means and geometric CV will be also shown.

Serum E6011 concentration vs time curves will be prepared. A serum concentration profile will be prepared for each subject and shown individually on a single plot per patient. A plot showing all serum profiles generated per treatment group will be prepared.

Summary serum E6011 concentration vs time profiles will also be prepared. A geometric mean serum profile will be shown by treatment group individually and grouped by treatment.

Pharmacodynamic data (serum total FKN concentrations, faecal calprotectin and serum CRP concentration measured values, change and % change from baseline) will be summarized by treatment group, evaluation time and race (all, Japanese and non-Japanese), including the number of sample results, minimum, medium, maximum, mean, standard deviation and coefficient of variation (CV). In addition, geometric means and geometric CV will be also shown.

Immunogenicity data (will be summarized by treatment group, evaluation time and race (all, Japanese and non-Japanese)) incidence and ratio of serum anti-E6011 antibodies are to be calculated by treatment group and evaluation time, and summarized including the number of sample results, minimum, medium, maximum, mean, standard deviation and coefficient of variation (CV). In addition, geometric means and geometric CV will be also shown.

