Subjects with less than 70 reduction in the CDAI (non-responders) at evaluation in Week 12 are to move on to the rescue period. The rescue period is to last 12 weeks, with additional administrations of 10 mg/kg of E6011 in Week 12, Week 13, Week 14 and every two subsequent weeks up to Week 22. Subjects with a reduction in the CDAI of 70 or more compared to baseline/Week 12 at evaluation in Week 24 of the rescue period are to move on to the open-label extension period. The extension period is to last 40 weeks, with 10 mg/kg of E6011 administered every four weeks from Week 24 to Week 60 and E6011 efficacy is to be evaluated at Week 64. Patients with less than 70 reduction in the CDAI compared to baseline and Week 12 at evaluation in Week 24 are to be discontinued.

[figure not shown]
The Principal Investigator or Sub-investigator is to confirm that the subjects' data as of Week 12 of the remission-induction period (double-blind) has been completely entered into the eCRF by the time the first evaluation in the rescue period or extension period takes place. Blinding in the double-blind period is to be maintained until a database in the double-blind study period is locked.

The post-observation period consists of an assessment in person 28 days after the completion or discontinuation of the extension period of the clinical trial, and an assessment in person or over the phone 70 days after the last administration of the IMP. The follow-up period entails contacting the patients over the phone, etc. every 6 months until 2 years have passed from the last administration of the IMP to inquire whether they have experienced progressive multifocal leukoencephalopathy (PML).

Date: 18-Apr-2022 version 11.0 Confidential Page 25 of 80

Figure 1 shows the design of the clinical trial.

Figure 1 Clinical trial design

Responders at CDAI evaluation on Week 12 of the remission-induction period are to move on to the extension period, in which E6011 is administered every four weeks. Non-responders are to move on to the rescue period, and if the CDAI has improved by Week 24, they are to move on to the extension period, in which E6011 administered every four weeks. Subjects whose CDAI has not improved by Week 24 are to be discontinued.

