6.8 Efficacy Analysis

Efficacy analysis will be based in the FAS and PPS populations. Primary analysis will be produced in the FAS population. Primary analysis will be repeated in the PPS population as a sensitivity analysis.

Efficacy analysis will be done for the remission-induction period and the entire administration period.

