The dose at baseline is calculated as the sum of doses in mg/day of all adrenocorticosteroids that are taken the baseline day. Doses at every visit are calculated as the sum of all adrenocorticosteroids taken from previous time point to the current visit date, for example, dose at week 2 is the sum of all doses taken from baseline to week 2 date.

Adrenocorticosteroids related to Crohn's disease will be identified as any concomitant corticosteroid at remission induction period in the database that has reported in the eCRF an indication to primary disease (Crohn's disease). Steroid free patients will be identified as patients that are taking any adrenocorticosteroid related to Crohn's disease at baseline and they stop taking them before week 12.

Subjects with missing secondary endpoint data due to premature discontinuation before 12 weeks after administration, or other reasons are treated as non-responders (NRI) in the modeling of the endpoints.

Secondary analysis will be performed in the FAS population and in the PPS population.

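### Response rates after Week 12 have no settled missing-data rule, and the SAP default drops Week 24 rescue failures from the Week 28–64 denominators

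*SAP*

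**What the plan says.** **Scope.** Long-term efficacy is a secondary objective (Protocol 8.2, SAP 3.3.2). CDAI and PRO2 response and remission rates are endpoints at every evaluation time (SAP 4.5.2). SAP 6.8 states: "Efficacy analysis will be done for the remission-induction period and the entire administration period".

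**Default for missing data.** SAP section 10 states: "Missing values will be tabulated with their frequency but will not be included in the calculation of percentages". It continues: "Analysis will be based on observed cases, i.e., no replacement of missing data is planned in general except otherwise planned". For those exceptions it points the reader to its sections 11, 12 and 14. Section 11 of the SAP is the reference list, and there is no section 12 or 14.

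**NRI in the SAP.** The sentence in 6.8.2 covers secondary data missing "due to premature discontinuation before 12 weeks after administration" or for other reasons. It says that such subjects "are treated as non-responders (NRI) in the modeling of the endpoints". The logistic models in 6.8.2 are specified at Week 12 only, and the descriptive rates listed there are at Weeks 2, 4, 8 and 12.

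**NRI in the protocol.** Section 9.7.1.6.2 has nearly the same sentence but applies NRI to the analysis of secondary endpoints, without limiting it to models. Section 9.7.1.10 asks for the induction-period efficacy analyses to be repeated for the entire dosing period. SAP 6.11 declares no departure from the protocol's statistical section.

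**Removal by rule.** Protocol 9.1 states: "Patients with less than 70 reduction in the CDAI compared to baseline and Week 12 at evaluation in Week 24 are to be discontinued". Sections 9.1.3 and 9.3.3 repeat this.

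**The concern.** After Week 24, part of the missing data is created by the protocol, and the trigger is lack of response. Dropping missing values from percentages then removes subjects already known to have failed. The printed rate describes those who stayed on treatment, whereas the secondary objective concerns long-term administration in the patients enrolled.

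Two programmers could also follow these documents in good faith and report different Week 52 rates. One would apply SAP section 10. The other would carry the protocol's NRI sentence forward.

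Tables are presented by induction treatment group (SAP 6.1). If Week 24 removals differ between former placebo and former E6011 subjects, the two columns would rest on differently selected subsets.

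**Working it through.** **1. Plan figures.** The documents give no long-term response rate, dropout rate or denominator, so there is no long-term figure to reproduce. The one design figure is the probability above 80% of confirming efficacy at Week 12, with 20 per group and a 40-point difference. It reproduces at 0.807 to 0.874 for placebo rates from 5% to 60%, and it has no bearing on this point.

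**2. Who is missing, and when.** From the schedules in Protocol Table 4:
- Weeks 16, 20 and 24 have CDAI in both tracks. Rescue non-responders are still present.
- Weeks 28 to 52 have CDAI in both tracks. Subjects removed at Week 24 are absent.
- Weeks 14, 56, 60 and 64 exist only for the rescue track.

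**3. Are the removed subjects known failures?** On the CDAI endpoints at Week 24, yes. A reduction from baseline below 70 fails both CR70 and CR100. Inclusion criterion 3 sets baseline CDAI at 220 or more, and 220 − 70 = 150, so a smaller reduction leaves CDAI above 150. Remission requires a value below 150. The rule does not settle their PRO2 status.

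**4. Direction.** Let n be the subjects due at a visit, m the missing and r the observed responders.
- Observed-case rate = r/(n − m).
- All-subject rate with NRI = r/n.
- Their ratio is n/(n − m), which is never below 1. It exceeds 1 whenever m > 0, and the rates then differ if r > 0.

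**5. Size, on assumed inputs.** Take N = 25, the enrolment in Protocol 9.7.2 (the FAS could be smaller). Assume a Week 12 CR70 share q of 30–70%, rescue success s of 20–60%, further extension dropout d of 0 or 20%, and a Week 52 observed-case rate of 70%.
- Removed at Week 24 = 25 × (1 − q) × (1 − s).
- Share observed at Week 52 = [q + (1 − q)s] × (1 − d).
- NRI rate = 70% × share observed.

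| q | s | d | Removed at Week 24 | Share observed | NRI rate | Gap to 70% (points) |
|---|---|---|---|---|---|---|
| 0.7 | 0.6 | 0 | 3 | 0.880 | 61.6% | 8.4 |
| 0.3 | 0.2 | 0 | 14 | 0.440 | 30.8% | 39.2 |
| 0.7 | 0.6 | 0.2 | 3 | 0.704 | 49.3% | 20.7 |
| 0.3 | 0.2 | 0.2 | 14 | 0.352 | 24.6% | 45.4 |

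**6. Whole-number example (assumed).** There are 12 Week 12 responders and 13 rescue subjects. Of the 13, 5 enter the extension and 8 are removed. At Week 52, 17 are observed and 12 have CR100: 12/17 = 70.6% observed-case, against 12/25 = 48.0% with NRI. At Week 64, suppose 3 of the 5 respond: 3/5 = 60% observed-case, against 3/13 = 23.1% of those who entered rescue. Dividing by the whole FAS would give 3/25 = 12%. That would be wrong, because it fails the 12 Week 12 responders at a visit they never had.

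**The case against.** The strongest reply is that the protocol already carries NRI forward. Its sentence covers the analysis of secondary endpoints, 9.7.1.10 repeats the efficacy analyses for the entire dosing period, and SAP 6.11 declares no change. In "Subjects with missing secondary endpoint data due to premature discontinuation before 12 weeks after administration, or other reasons are treated as non-responders (NRI", the 12-week limit can be read as attaching only to premature discontinuation, which leaves the closing catch-all without a time limit. This stands in part: a reader might infer that the plan has chosen observed cases for the long term, and the documents do not establish that. But the SAP sentence stops at modelling, so its descriptive long-term rates still fall under section 10. If the protocol is read broadly, the two documents differ and 6.11 does not say so.

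Other stronger readings also go too far:
- A reader might infer that every percentage after Week 12 is computed among selected responders. Weeks 14 to 24 still include rescue non-responders. The Week 24 rule removes no Week 12 responder. Entry from rescue needs a 70-point fall from baseline or from Week 12, so entrants need not be CR70 responders against baseline.
- A reader might infer that observed-case rates will rise over time. No listed rule removes subjects for losing response in the extension, and such losses would lower the rate.

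The stakes are also limited. The analyses are exploratory and mainly descriptive (SAP 6.1). All treatment after Week 12 is open-label E6011, so no placebo-controlled comparison is distorted. Missing counts are tabulated, and SAP 6.3 reports discontinuations by reason, including insufficient effect after rescue. A percentage clearly labelled as among continuing subjects would not be wrong in itself. These points lower the severity, but they do not supply a denominator.

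**Conclusion.** The point holds as an unresolved rule whose default works in a known direction. Following the SAP as written, subjects discontinued at Week 24 for lack of response leave the Week 28–64 denominators, and observed-case rates are at or above all-subject rates at those visits. The direction is certain. The size is not: 8 to 45 points at Week 52 is an illustration resting wholly on the assumed response, rescue and dropout rates, not an estimate for this trial. The documents do not support saying that long-term efficacy will be overstated by any stated amount. NRI is explicit for the Week 12 primary analysis (SAP 6.8.1), which is unaffected. The change should be made before the entire-administration-period database is locked.

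**What to change.** In SAP 6.8:

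1. Define the long-term binary efficacy rate at end of treatment: Week 52 for Week 12 responders and Week 64 for the rescue track. The denominator is all FAS subjects by randomised group. Count Week 24 discontinuations for lack of response, and all other dropouts, as non-responders.
2. For by-visit CDAI and PRO2 rates, use the FAS at visits scheduled for both tracks, and subjects who entered rescue at the rescue-only visits (Weeks 14, 56, 60, 64), with the same NRI rule. A whole-FAS denominator at every visit should not be used. Extension-period colonoscopy is scheduled at Week 52 in one track and Week 64 in the other, so for SES-CD only the end-of-treatment rate applies.
3. Show observed cases beside each rate, with the number at risk.
4. Align the NRI sentence in SAP 6.8.2 with Protocol 9.7.1.6.2, or record the difference in SAP 6.11.
5. Correct the cross-references in SAP section 10.

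The cost is SAP wording and one extra table column. The downside for the sponsor is lower headline long-term rates.
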